3.6 Participant Timeline

Figure 1. Participant Timeline and Flow

All Participants

Day 14:

- Anthropometry (height, weight, MUAC)
- Adverse Events
- Vital Status
- Malaria (thin and thick smears) and temperature
- Whole Blood Venipuncture
- NP Swab
- Fresh Frozen Stool
- Rectal Swab

Day 180 (Includes window of 120-210 days):

- Anthropometry (height, weight, MUAC)
- Vital Status
- Malaria (thin and thick smears) and temperature
- Whole Blood Venipuncture
- NP Swab
- Fresh Frozen Stool
- Rectal Swab

Day 730 (2 Year Follow-Up)

- Rectal Swab

4 Chapter 4: Procedures

Table 1 provides an overview of all study procedures. The eligibility assessment, enrollment, and randomization are explained in Chapter 3. See the appendix for all study forms described in the table.

Table 1: Overview of Procedures

Day (since treatment)	Activity	Study Form
Day 0, 2,4,6,8,10,12, 14, 180	 Treatment  Rectal swab for 50 randomly selected children	 Form 1: Eligibility  Form 2: Baseline  Form 6: Treatment  Form 8: Rectal Swab Cohort
0 (Baseline)	 Eligibility Assessment  Enrollment  Randomization  Anthropometry  Whole Blood  Blood Smear  Temperature  NP swab  Rectal Swab  Fresh Frozen Stool  Treatment	 Form 1: Eligibility  Form 2: Baseline  Form 4: Exams  Form 6: Treatment
Day 7	 IHPS follow-up on neonates	 Form 7: IHPS
Day 14	 Anthropometry  Whole Blood  Blood Smear  Temperature  NP swab  Rectal Swab  Fresh Frozen Stool  IHPS follow-up on neonates  Vital Status  Adverse Events survey	 Form 3: Follow-up Registration  Form 4: Exams  Form 7: Vital Status,AE, IHPS
Day 21	IHPS follow-up on neonates	 Form 7: IHPS
Day 180 (primary outcome) *Includes window of 120-210 days	 Anthropometry  Whole Blood  Blood Smear  Temperature  NP swab  Rectal Swab  Fresh Frozen Stool  Vital Status	 Form 3: Follow-up Registration  Form 4: Exams  Form 7: Vital Status,AE, IHPS

Day 730 (2 Year Follow-Up)	 Rectal Swab	 Form 4: Exams
----------------------------	--------------------------------------	--

4.1 Treatment

Details on the study medication are provided in Chapter 5. No child will be treated before 8 days of life or after 59 months. Once the child is treated, a team member will record if the treatment was given or if the child did not receive treatment. If the child was not treated, the team member will provide the reason why the child was not treated.

4.2 Field Worker Safety Assessment

3 weekly home visits will be performed by a field worker for any participants younger than 28 days old at the time of treatment. The visits will be performed 7, 14, and 21 days after treatment. Specifically, the team will be asking a series of questions to the parent or guardian in an attempt to screen for infantile pyloric stenosis. See Chapter 6 for more information on IHPS. The field worker will ask if the child has vomited since treatment, if the vomit was projectile, and if the child is gaining or losing weight. Those who answer affirmatively will be referred to the study pediatrician for closer examination and follow-up.

All caregivers will be given a pamphlet in the local language explaining IHPS in detail. Contact information and instructions on what to do if the child presents symptoms will also be provided.

4.3 GAMIN QUOD: Rectal Swab Home Visits

50 children enrolled in the study will be randomly selected to provide additional rectal swabs at days 0, 2, 4, 6, 8, 10, 12, 14, and 180 days after treatment. We will select 25 children per study arm and conduct a home-visit for these given days.

4.4 Anthropometry Assessment

We will record every participant's weight, length/height, and mid-upper arm circumference at baseline, day 14, and day 180 after treatment. Weight will be measured using the SECA scale. Length/height will be measured using a Shorrboard to the nearest cm. See chapter 9 for the anthropometric measurements protocol.

4.5 Whole Blood

Every participant will undergo a blood drawl procedure at baseline, day 14, and day 180 after treatment. Venipuncture will be done by a trained professional using a sterile butterfly-winged needle. See chapter 8 for the venipuncture protocol.

4.6 Blood Smears

Thick and thin blood smears will be collected for every enrolled child at baseline, day 14, and day 180 after treatment. The child's finger will be pricked with a lancet by a trained professional. We will use the smears to determine the child's malaria status. Additionally, we will record the child's core body temperature. If the child has a fever, we will administer a rapid diagnostic test. If the child is positive for malaria, we will give the child a referral to the health center. See chapter 8 for more on the blood protocol.

The RDT utilized depended on local availability. The brand used is described below:

SD Bioline Malaria PF (PfHRPII) from November 19-28, 2019 for baseline (407 children)

CareStart malaria PF (PfHRPII) from November 29-30, 2019 for baseline (43 children)

Onsite (PfHRPII and pLDH) from December 3-16, 2019 for day 14 visits.

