4.11 Summary of Sample Collections

Summary of laboratory and other assessments in Nouna longitudinal study

Organism/Outcome	Test	Sample	Time Point (Days)			Processing Site
			0	14	180	
Malaria	Thick and Thin Blood Smears	Finger stick	✓	✓	✓	Nouna
Phenotypic resistance: S. pneumoniae	Kirby Bauer (or Etest)	NP swabs	✓	✓	✓	Nouna
Genotypic resistance: E. coli , S. pneumoniae , S. aureus , Campylobacter spp Klebsiella spp	Targeted PCR: erm , mef , mph	Rectal and NP swabs	✓	✓	✓	UCSF
Microbiome	Next-generation sequencing	Rectal and NP swabs	✓	✓	✓	UCSF
Inflammatory markers	C-reactive protein	Whole blood and frozen stool	✓	✓	✓	Nouna and/or Gates labs
IgA-bound bacteria from small intestine	BugFACS	Whole blood and frozen stool	✓	✓	✓	Gates labs
Nutritional status	Anthropometric measurements	Weight, height, MUAC	✓	✓	✓	Nouna
Vital status	Mortality, hospitalization	Caregiver questionnaire		✓	✓	Nouna

5 Chapter 5: Study Medication

Enrolled participants will be offered weight-based, directly observed, oral suspension azithromycin or placebo. Adverse events will be monitored.

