7.1.2 Fingerstick Procedure

Inform the mother that her child's finger will be pricked to obtain blood to test for malaria and anemia. Describe the finger prick procedure, reassure her, and answer all questions. The blood specimen should be collected as described below to minimize the discomfort of the child and to ensure sufficient blood volume collection.

A finger stick of capillary blood will be collected for thin and thick blood smears to assess for malaria. Blood will be collected by a gloved health worker using aseptic technique. Gloves will be changed between each participant. The fingerprick or heelstick site will be disinfected using a 70% isopropyl alcohol swab.

1. Prepare the disposable lancet. Use a NEW disposable lancet for each child. **Do not** re-use lancets!
2. The recorder will scan the child's QR code, and place a random number sticker on the TropBio filter paper and the (right edge of the) slide.
3. Position the child for the finger stick. Make sure that the child's right hand is warm and relaxed. Hold the child's thumb, middle, or ring finger on his/her right hand (from the top of the knuckle to the tip of the finger) between your left thumb and finger and disinfect in small outward circles with an individually packaged alcohol wipe.
4. After the alcohol dries, use the thumb to lightly press the child's thumb or finger from the top of the knuckle towards the fingertip to stimulate blood flow towards the sampling point (puncture site). For the best blood flow and least pain, prick the side of the thumb/fingertip, not the center. While applying light pressure towards the thumb/fingertip, hold the lancing device in your hand and prick the thumb/finger. If the finger prick is performed properly, a single prick should be sufficient to collect the required amount of blood.
5. Allow the blood to ooze out. Wipe away the first 2 or 3 drops of blood with gauze. If necessary, re-apply light to moderate pressure towards the thumb/fingertip (approximately 1 cm behind the site of the finger prick) until another drop of blood appears.
Note: **Do not** squeeze forcefully. Avoid "milking" as it may dilute the blood with tissue plasma.

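### Protocol 4.6 orders a malaria RDT only for febrile children, while the SAP's primary RDT comparison presupposes a day-14 result in essentially every child; the two need reconciling

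*Protocol*

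**What the plan says.** **Protocol.** Section 4.6 gives smears to everyone: "Thick and thin blood smears will be collected for every enrolled child at baseline, day 14, and day 180 after treatment". It uses those smears to determine malaria status. The RDT comes in only through the sentence "If the child has a fever, we will administer a rapid diagnostic test", and the sentence after that deals with referral of children who are positive for malaria.

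The other places that list malaria procedures name smears and not the RDT:
- the visit lists in 3.6 ("Malaria (thin and thick smears) and temperature");
- Table 1 in Chapter 4;
- the assessment summary in 4.11 ("Thick and Thin Blood Smears");
- the fingerstick procedure within 8.1 ("A finger stick of capillary blood will be collected for thin and thick blood smears to assess for malaria").

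Section 4.6 also records which RDT brands were used. Two brands are listed for baseline, with 407 and 43 children, over November 19-30, 2019. One brand is listed for day 14, with dates but no number of children: "Onsite (PfHRPII and pLDH) from December 3-16, 2019 for day 14 visits".

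**SAP.** Section 1.1 puts RDT positivity over 14 days first among the objectives, for children aged 8 days to 59 months. Section 2.1.1 compares RDT positivity between arms by logistic regression as a primary analysis, and adds a subgroup of children RDT-negative at baseline who are compared at day 14. Neither analysis mentions fever. Section 3 assumes 225 per group, no loss to follow-up, 10% positivity in control and 80% power, and gives a detectable difference of -0.0659.

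**The concern.** The endpoint that carries the SAP's sample size depends on a test which the protocol, as written, gives only to children with fever. Temperature at day 14 is measured after randomisation and may be affected by treatment. If the fever rule decided who was tested at that visit, RDT results would exist only for children selected on that symptom. The arms would no longer be compared as randomised, and the number analysed would not be the 225 per group behind the power statement. The baseline-negative subgroup would be affected as well, since it needs an RDT result at both visits.

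**Working it through.** **1. Reproduce the SAP's figure.** The inputs from SAP section 3 are n = 225 per group, control 10%, difference -0.0659 (so 3.41% on azithromycin) and power 80%. Section 3 does not state the test level; two-sided 0.05 is assumed. With pooled variance under the null:

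n per group = [1.96 × √(2p̄(1 − p̄)) + 0.8416 × √(p1(1 − p1) + p2(1 − p2))]² / (p1 − p2)²

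- p̄ = (0.10 + 0.0341)/2 = 0.06705
- first term: 1.96 × √0.12511 = 0.693
- second term: 0.8416 × √0.12294 = 0.295
- n = (0.693 + 0.295)² / 0.0659² ≈ 225

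Power at 225 per group is 0.800, so the SAP's arithmetic is correct. It is correct for 225 RDT results per arm, which is all 450 children.

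**2. What baseline shows.** 407 + 43 = 450 = 2 × 225, the SAP's full enrolment. The revision history dates the fever sentence to 4/15/19, so it was already in place in November 2019. Under a fever-only rule, all 450 children would have had to be febrile at baseline. Testing regardless of temperature is the far more natural reading.

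**3. What day 14 shows.** November 19 + 14 days = December 3, and November 30 + 14 days = December 14. The recorded period of December 3-16 covers the whole expected window. That fits testing of every child, but a brand and a date range would look the same if only febrile children were tested.

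**4. Is there an express provision elsewhere?** SAP 2.1.1 says that indicators are collected by finger prick and stool at days 0, 14 and 180, but it does not name the RDT, and the protocol's finger prick is described for smears. No passage supplied orders a day-14 RDT for every child.

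**5. Can a power loss be stated?** No. The tested shares and the positivity among febrile children below are assumptions that appear in neither document. The relative effect is held at 3.41/10 = 0.341, with the same formula and two-sided 0.05.

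| Tested per arm (assumed) | Control 10% | Control 20% (assumed) | Control 30% (assumed) |
|---|---|---|---|
| 113 (half) | 0.51 | 0.83 | 0.96 |
| 45 (one fifth) | 0.24 | 0.45 | 0.65 |

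Depending on the assumptions, power falls well below 80% or rises above it. What would remain in every cell is selection on a post-randomisation symptom.

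**The case against.** The strongest reply is that the fever sentence never limited the outcome test. It stands next to the referral instruction and reads as clinical care, and the 450 baseline tests were done while it was in force. The missing day-14 count also has an ordinary explanation: baseline used two brands, so the children had to be split between them, whereas day 14 used one and there was nothing to split. The lists in 3.6, Table 1, 4.11 and 8.1 omit the RDT altogether, including the baseline tests known to have been done, so they cannot show who was tested. The study forms and the Manual of Operations that the SAP relies on are not among the documents here, and either may contain the RDT procedure. Finally, the SAP never says in words that every child must be tested, and it has a rule for missing outcomes.

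Most of this stands, and it makes universal day-14 testing the likelier practice. It does not remove the inconsistency. The requirement for near-complete testing is an inference, but one that follows from an unrestricted comparison sized on 225 per group with no loss. If all 450 children were tested at baseline, the rule written in 4.6 does not describe how the outcome RDT was given, and that is reason enough to correct the text.

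A reader might go further and infer that day-14 RDTs were in fact done only in febrile children, or that the trial has only 51% or 24% power. The documents support neither. No passage shows restricted testing at day 14, and those power values depend on assumed tested shares and on keeping 10% versus 3.41% among febrile children.

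**Conclusion.** The concern holds as a minor to moderate inconsistency between protocol and SAP. The written RDT rule is conditional on fever; the SAP's primary RDT comparison, its baseline-negative subgroup and its power statement presuppose results in essentially all children at days 0 and 14. The SAP's figure of -0.0659 is right on its own terms, assuming a two-sided 0.05 test.

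If every child was tested at day 14, the analysis and its power stand, and the correction is to the text and the reporting. If the fever rule was applied at day 14, the comparison is conditional on a post-randomisation symptom and the power statement is void. The available evidence favours the first case without settling it. No size of bias or loss of power is claimed.

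**What to change.** - **Protocol.** Reconcile 4.6, Table 1 and 4.11 with the SAP, so that the outcome RDT at days 0 and 14 is described separately from any fever-triggered test. The fever-triggered test and its referral are left as they stand.
- **SAP.** Define the day-14 RDT analysis population as all randomised children seen at day 14, regardless of temperature. Report the number RDT-tested per arm, and apply the SAP's existing missing-outcome rule to children without a result.
- **Only if the records show that day-14 RDTs were limited to febrile children.** Label the RDT result as conditional on fever, withdraw the power statement, and base the whole-arm malaria comparison on the smears the protocol already collects from every child. Enter the change, with its date, in the SAP change log.

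The cost is a few wording changes and a count of day-14 RDTs per arm from the electronic records. No new sampling is needed. The smear fallback depends on the slides having been read.

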4.7 Swabs

Nasopharyngeal and rectal swabs will be collected from each participant at baseline, day 14, day 180, and 2 years after treatment. Flocked pediatric swabs will be used for the NP collection. See chapter 6 for more information on the swab protocol.

4.8 Stool

We will collect fresh frozen stool from participants at each visit. Infants will be given a diaper to produce the sample while older children will be provided with miniature potties. The potties will have plastic bags placed around the opening to catch the sample. More details about stool collection are found in chapter 8. The potties will be sanitized after each use.

At baseline, children that cannot produce the sample will be asked to stay at the hospital for up to 2 hours. At the follow-up visits, the field team will schedule appointments for the child to come back and produce the sample. Alternatively, the field team will go to the child's home to obtain the sample. The sample will then be placed in RTIC coolers and immediately transported back to the laboratory freezer.

4.9 Vital Status Assessment

A vital status assessment will be conducted at each follow-up visit (days 14 and 180). Field workers will record on the tablet if the child is alive, died, moved, or unknown. Vital status will also be conducted during the neonatal follow-up visits at days 7, 14, and 21 after treatment.

4.10 Adverse Events

At the 14-day follow-up visit, field workers will conduct a survey of adverse events, including if the child had any of the following symptoms:

- Fever

- Diarrhea
- Vomiting
- Abdominal pain
- Skin rash
- Constipation

The field worker will also assess if the caregiver had sought care for the child since the last time they spoke to the study team, and if so, what the reason for the health care visit and if the child was hospitalized.

4.11 Summary of Sample Collections

Summary of laboratory and other assessments in Nouna longitudinal study

Organism/Outcome	Test	Sample	Time Point (Days)			Processing Site
			0	14	180	
Malaria	Thick and Thin Blood Smears	Finger stick	✓	✓	✓	Nouna
Phenotypic resistance: S. pneumoniae	Kirby Bauer (or Etest)	NP swabs	✓	✓	✓	Nouna
Genotypic resistance: E. coli , S. pneumoniae , S. aureus , Campylobacter spp Klebsiella spp	Targeted PCR: erm , mef , mph	Rectal and NP swabs	✓	✓	✓	UCSF
Microbiome	Next-generation sequencing	Rectal and NP swabs	✓	✓	✓	UCSF
Inflammatory markers	C-reactive protein	Whole blood and frozen stool	✓	✓	✓	Nouna and/or Gates labs
IgA-bound bacteria from small intestine	BugFACS	Whole blood and frozen stool	✓	✓	✓	Gates labs
Nutritional status	Anthropometric measurements	Weight, height, MUAC	✓	✓	✓	Nouna
Vital status	Mortality, hospitalization	Caregiver questionnaire		✓	✓	Nouna

5 Chapter 5: Study Medication

Enrolled participants will be offered weight-based, directly observed, oral suspension azithromycin or placebo. Adverse events will be monitored.

5.1 Study Medication Description

Zithromax® for oral suspension is supplied in bottles containing azithromycin dehydrate powder equivalent to 1200mg per bottle and the following inactive ingredients: sucrose; tribasic anhydrous sodium phosphate; hydroxypropyl cellulose; xanthan gum; FD&C Red #40; and flavoring including spray dried artificial cherry, crème de vanilla, and banana. After constitution, a 5mL suspension contains 200mg of azithromycin.

5.2 Dosage Information

All children will receive a single dose of azithromycin or placebo. Dosage will be weight-based, based on the baseline weight assessment as part of the anthropometry measurements. Dosing will follow the WHO recommendations for treatment of active trachoma:

- Single dose of 20mg/kg in children (up to the maximum adult dose of 1g)

Children who are allergic to macrolides/azalides will be excluded from this study.

5.3 Medication Procurement

Study medication will be procured in the United States and shipped to the study site. All medications will be prepared as an oral suspension. Participants will not incur any costs associated with the study or the study medication.

5.4 Medication Quality Control

The study medication will be stored at the Centre de Recherche en Sante de Nouna in a temperature monitored storage room. The Nouna team and site staff will regularly check the expiration dates and all expired medication will be discarded appropriately. The study coordinator will ensure the hospital has adequate stock of study medication.

5.5 Directly Observed Treatment

Each child will take the oral suspension of azithromycin or placebo under direct observation by a hospital staff member. All doses will be electronically recorded on the study tablet.

5.6 Adverse Events

Azithromycin is generally well tolerated. The most common side effects include abdominal pain, diarrhea, and vomiting. These symptoms occur in less than one in twenty people who receive it. Additional side effects are rare, but include allergic reactions and abnormal liver function.

Diarrhea due to *Clostridium difficile* has been reported in uncommon cases.

At each monitoring visit, staff members will screen all enrolled children for any adverse events. Parents or guardians of the participants will be advised to report any adverse events by phone or in person. Study staff will inquire about the child's experience of adverse events during each follow-up visit and record if the child has had any of the following symptoms:

- Fever
- Diarrhea
- Vomiting
- Skin rash
- Constipation
- Abdominal Pain

The study team will also inquire whether the parent or guardian sought care for the child since the last monitoring visit. If so, the team will find out what the reason for the health care visit was and if the child was hospitalized.

The definition of serious adverse events will include death, hospitalization, or any other life-threatening situation. Within 24 hours, serious adverse events must be reported to the Medical Monitor. The study team member conducting the follow-up visit must email [name], the Director of CRSN, who will immediately email the Medical Monitor and UCSF team. The Medical Monitor will evaluate the adverse event and determine if the event could be reasonably

related to azithromycin and report the results of this determination to the investigators and the DSMC. All information on adverse events, both serious and non-serious, will be kept on data collection forms through the mobile application.

5.7 Background on Infantile Hypertrophic Pyloric Stenosis in Neonates

IHPS is a condition in which the pylorus of the stomach becomes thickened, resulting in gastric outlet obstruction.⁸ In developed countries, the incidence of IHPS is approximately 2 per 1,000 infants in the general population. While surgery is generally curative, the condition is lethal in the absence of surgery. The cause of IHPS is unknown and likely complex, and both genetic^{9,10} and environmental^{11,12} factors are thought to contribute to its development. Male neonates are disproportionately affected by IHPS, with a 4-5:1 male to female ratio.^{8,10,11} Other risk factors for IHPS include prone sleeping position, bottle/formula feeding,^{12,14,15} preterm birth^{11,12} cesarean section delivery^{11,12} and birth order.^{8,11-13} IHPS incidence appears to be decreasing over time, which some have attributed to public health interventions promoting supine sleeping position and exclusive breastfeeding.^{16,17}

In addition to genetic and environmental factors, erythromycin is associated with increased risk of infantile hypertrophic pyloric stenosis (IHPS).¹⁸ Given that azithromycin is a related compound, there is some concern that azithromycin may lead to increased risk of IHPS in neonates. Limited evidence exists of the risk of IHPS among neonates treated with azithromycin.¹⁹ Two randomized controlled trials have assessed the use of intravenous azithromycin for prevention of bronchopulmonary dysplasia (BPD) in low birthweight infants (<1,250g) compared to placebo within 72 hours of birth.^{20,21} Of 263 neonates enrolled in the two studies (N=130 receiving IV azithromycin), no cases of IHPS were reported. A third non-placebo controlled randomized trial of azithromycin prophylaxis for BPD in premature neonates additionally reported no cases of IHPS among 53 neonates receiving azithromycin.²² An observational study of 58 infants receiving azithromycin following exposure to a healthcare worker with pertussis did not identify any cases of IHPS.²³ The largest study of azithromycin exposure in neonates is a retrospective cohort of more than one million infants in the TRICARE Management Activity military health system, which reported an overall IHPS rate of 2.3 per 1,000 (95% CI 2.2 to 2.4) among children in the first 90 days of life.²⁴ Of 4,875 infants prescribed azithromycin, there were 8 cases IHPS, 3 of which occurred when azithromycin was prescribed during the first 14 days of life and 5 of which during the first 15-42 days of life. Overall, there was no significant difference in IHPS rate in infants treated with azithromycin versus IHPS rates among infants who had not received an antibiotic during the first 90 days of life were not presented by time since birth. Table 2 lists the rates of IHPS following azithromycin, erythromycin, or cephalexin prescription.

Table 3: Unadjusted rate of IHPS in infants with oral azithromycin, per 1,000

	Azithromycin	Erythromycin	Cephalexin
0-14 days ¹			2.2 (0.05-12.2)
15-42 days ¹	20.3 (4.2-59.2)	30.9 (14.1-58.7)	3.1 (1.0-7.2)
43-90 days ¹	6.9 (2.2-16.1)	9.3 (3.0-21.8)	0 (0-1.6)
Overall	1.6 (0.7-3.2)	8.9 (5.2-14.3)	3.0)

There is relatively little evidence of the epidemiology of IHPS in sub-Saharan Africa. A study in Nigeria documented 57 cases of IHPS from 1978-2008 at a university teaching hospital, with only a single case from 2003-2008.¹⁷ A study of 102 cases of IHPS over a 5-year period in Tanzania documented a 4.9% mortality rate despite surgical intervention.²⁶ The risk of mortality was higher in infants under 2 weeks of age and those with delayed presentation to care. A retrospective study at a tertiary hospital in Ethiopia found that 12.9 per 1,000 admissions were due to IHPS, with a 3.3% mortality rate.¹³ In Ouagadougou, an unpublished case series of 32 infants treated for IHPS showed a 6.3% mortality rate, which was attributed to late presentation due to the infant traveling from far outside the city.

